LY3526318 is a small molecule that inhibits transient receptor protein ankyrin 1 (TRPA1), a calcium permeable nonselective cation channel. There is strong clinical and preclinical evidence for TRPA1 antagonism in the alleviation of chronic pain. In humans, exogenous TRPA1 agonist administration induces pain and nerve hyper-excitability. TRPA1 antagonists have been safe and well tolerated in healthy participants (ODM-108; NCT02432664) and in patients with diabetic neuropathy (GRC-17536; EU Clinical Trial Register 2012-002320-33). GRC-17536 has been efficacious for pain relief in a Phase 2a trial in a subset of patients. LY3526318 has been demonstrated to be safe and well tolerated in Study CVAA. The effect of LY3526318 on cinnamaldehyde (CA)-induced dermal blood flow (DBF) will be compared to placebo.

Objectives/Endpoints:

Objectives	Endpoints
Primary	
To assess target engagement of TRPA1 after a single dose of LY3526318	Decrease in CA-induced dermal blood flow (DBF) relative to placebo measured by laser Doppler Imaging (LDI) at 3 hours post-dose
Secondary	
To evaluate the safety and tolerability in healthy females following single oral doses of LY3526318	
 • Treatment-emergent adverse events • Serious adverse events
To assess target engagement of TRPA1 after a single dose of LY3526318 using an alternate imaging method	Decrease in CA-induced DBF relative to placebo measured by Laser Speckle Contrast Imaging (LSCI) at 3 hours post-dose
To assess the pharmacokinetics of LY3526318 following single oral doses of LY3526318	Summary of LY3526318 plasma concentrations by dose and time point

Summary of Study Design, Treatment Arms and Planned Duration for an Individual Participant:

Study CVAB is a randomized, double-blind, placebo-controlled, 4-way crossover study of LY3526318 in healthy female participants.

All participants will have 2 screening visits with the first to evaluate the health of the participant and the second visit to undergo a laser Doppler imaging (LDI) assessment to ensure a response of at least 100% increase in DBF between pre- and post-CA challenge. Following a screening period of up to 28 days, eligible participants will be confined to the clinical research unit (CRU) from Day -1 until all assessments are completed on Day 2 of each dosing period.

Each participant will be randomly assigned to receive 4 unique doses of study drug in a ratio of 3 LY3526318: 1 placebo, in a crossover manner with at least 6 days of washout between doses. The planned dose levels of LY3526318 will be between 10 and 100 mg.

The LDI and laser speckle contrast imaging (LSCI) assessment will be performed at approximately 3 hours and 24 hours following study drug administration. The change in DBF before and after CA application will be compared between LY3526318 and placebo.

All participants will attend scheduled visits at the CRU for follow-up safety assessments.

Number of Participants:

Sufficient number of participants will be screened to achieve 16 randomized participants.

Statistical Analysis:

For the primary endpoint, summary statistics for each cohort will be provided by treatment.

All participants who receive at least one dose of study drug and for whom the data are considered sufficient and interpretable will be included in the analyses. Additional exploratory analyses will be conducted as deemed appropriate. For continuous variables, summary statistics will include number of participants, mean, median, standard deviation, minimum, and maximum. Categorical endpoints will be summarized using number of participants, frequency, and percentages.

Plasma concentration data will be summarized and may be combined with pharmacodynamic (PD) data and pharmacokinetic (PK) data from Study CVAA, to perform population PK/PD analyses in order to inform the design of future studies.

2. Schedule of Activities

	S		Treatment Period 1				Treatment Period 2				Treatment Period 3				Treatment Period 4			FU	ED ^d	
Study Day	≤28		-1 ^b	1	2	8	14 ^b	15	16	22	28 ^b	29	30	36	42 ^b	43	44	50	-	
Visit Window (days)	-		-	-	-	±1	-	-	-	±1	-	-	-	±1	-	-	-	±2	-	
Visit	1 ^a	2 ^a	3 ^c				4	5 ^c				6	7 ^c				8	9 ^c		10
Admit to CRU			X				X				X				X					
Discharge from CRU					X				X				X					X		
CRU visit	X	X				X				X				X				X	X	
Informed consent	X																			
Medical history	X																			
Height	X																			
Weight	X		X															X	X	
Physical examination	C		D	D	D	D	D	D	D	D	D	D	D	D	D	D	D	C	C	
Urine drug screen and ethanol test	X		X				X				X				X			X	X	
Hematology and clinical chemistry	X			P	24h			P	24h			P	24h			P	24h	X	X	
Urinalysis ^e	X			P														X	X	
β-hCG pregnancy test	X		X			X	X			X	X			X	X			X	X	
C-SSRS	X		X				X				X				X			X	X	
Vital signs including temperature	X			P and 3h	24h			P and 3h	24h			P and 3h	24h			P and 3h	24h	X	X	
ECG ^f	X			P and 3h	24h			P and 3h	24h			P and 3h	24h			P and 3h	24h	X	X	
Randomization				X																
Study drug administration ^g				X				X				X				X				
PK blood sample ^h				P and 3h	24h	X		P and 3h	24h	X		P and 3h	24h	X		P and 3h	24h	X	X	
DBF by LDI ^{a,i}		X																		
DBF by LDI and LSCI ⁱ				P and 3h	24h			P and 3h	24h			P and 3h	24h			P and 3h	24h			
AE / Con Med	↔ X ↔																			

Abbreviations: AE = adverse events; C = compete physical examination; Con Med = concomitant medications CRU = clinical research unit; C-SSRS= Columbia-Suicide Severity Rating Scale; D = directed physical examination; DBF = dermal blood flow; ECG = electrocardiogram; ED = early discontinuation; FU = safety follow-up; h = hour; LSCI = laser speckle contrast imaging; LDI = laser Doppler imaging; P = pre-dose assessment; PK = pharmacokinetic; S = Screening.

Note: In the event that assessments are planned for the same time, assessments should be conducted in following order: LSCI DBF assessment, LDF DBF assessment, PK sample, and ECG/vital signs. The PK sample should be collected as soon as the LDI/LSCI DBF assessment is completed. The ECG and vital signs measurement should be obtained at least 30 minutes after the PK sample is drawn.

- a Screening visits will be performed within 28 days before the administration of first dose. All participants will have 2 screening visits with the first to evaluate the health of the participant and the second visit to undergo the LDI DBF assessment.
- b Can be performed on a day prior to dosing or pre-dose on day of dosing.
- c All participants will remain in the CRU until completion of all procedures that occur the day following each dose.
- d Participants who discontinue the study prior to study completion will complete the ED visit procedures.
- e A standard urine dipstick may be used.
- f A single 12 lead ECGs will be obtained in the supine position after at least 10 minutes rest.
- g Study drug will be administered in a fasting state (8 hours pre-dose until 4 hours post-dose). The exact time study drug is administered will be recorded.
- h The timing of PK sample collections may be adjusted based on clinical needs. The exact sample collection dates and times must be recorded.
- i All participants will have an LDI and LSCI procedure with cinnamaldehyde challenge to measure DBF at stipulated time points. The pre-dose measurement will include at least 30 minutes of acclimatization, followed by a dermal blood flow measurement, without cinnamaldehyde application. Each post-dose measurements will include at least 30 minutes of acclimatization, followed by a pre-cinnamaldehyde dermal blood flow measurement (about 10 minutes before cinnamaldehyde application). Next, cinnamaldehyde will be applied and a post-cinnamaldehyde measurement at 20 minutes following the cinnamaldehyde application will be performed. The LDI assessment will be performed following completion of LSCI assessment.

3. Introduction

3.1. Study Rationale

LY3526318 is a small molecule designed to inhibit transient receptor protein ankyrin 1 (TRPA1), a calcium-permeable nonselective cation channel, expressed by peripheral pain-sensing nociceptors, which play a pivotal role in generation of pain (Maatuf et al. 2019). A nonclinical efficacy pharmacology study using a formalin-induced flinch model in rats showed an analgesic effect after a single dose of LY3526318. The potential of LY3526318 to produce unwanted pharmacological effects associated with central nervous system (CNS), cardiovascular, or respiratory functioning was determined in rats, monkeys, and *in vitro* systems (see Section 3.2).

As on September 2019, LY3526318 or matching placebo has been administered to 40 healthy participants in the single ascending dose (SAD) portion of the first-in-human (FIH) study J2D-MC-CVAA [CVAA]. In CVAA, single LY3526318 doses between 10 mg and 300 mg have been found to be safe and well tolerated. This CVAB study is intended to demonstrate target engagement of TRPA1 measured by dermal blood flow (DBF) response to cinnamaldehyde (CA) with LDI.

3.2. Background

Chronic pain is a major health issue affecting the quality of life of millions of patients. Nonsteroidal anti-inflammatory drugs are the primary choice of drugs for chronic pain treatment; however, efficacy is limited in many patients. Opioids are potent but cause sedation and have addictive potential, relegating them to third- and fourth-line treatment options in chronic pain (Ko et al. 2019).

The role of TRPA1 in pain and inflammation and its localization in sensory neurons has been characterized (Bodkin and Brain 2011; Ückert et al. 2017). TRPA1 agonists evoke pain and an adverse response when administered exogenously (Berta et al. 2017; Demartini et al. 2017; Maatuf et al. 2019; Wang et al. 2019). Additionally, there is genetic evidence for the contribution of TRPA1 to chronic pain (Kremeyer et al. 2010).

TRPA1 antagonists are undergoing evaluation in clinical trials, where there is evidence of efficacy and safety (ODM-108, NCT02432664; GRC 17536, EU Clinical Trial Register 2012-002320-33).

The results of the general toxicology studies, the behavioral and cardiorespiratory safety pharmacology studies, the *in vitro* human ether-à-go-go channel assay, and the *in vitro* and *in vivo* genotoxicity/mutagenicity battery justified proceeding to human clinical studies.

A CNS safety pharmacology study in the rat and a cardiovascular respiratory study (Study # 00926046) in monkeys showed no adverse findings up to the highest dose (300 mg/kg) of LY3526318 tested. No test article-related toxicity was seen at any dose in the 28 day repeat-dosing study in monkeys (Study # 00926044; highest dose was 1000 mg/kg/day) CC1

CCI

Ongoing review of the blinded data from the CVAA study indicated that single oral doses of LY3526318 or placebo at studied dose levels (10, 50, 100, 200 and 300 mg) were safe and well tolerated. All reported adverse events (AEs) were nonserious and mild in severity. No clinically significant observations were reported in clinical laboratory, vital signs, and electrocardiogram (ECG) data. Single dose administration of LY3526318 in the 10 to 300 mg dose range resulted in measurable LY3526318 concentrations.

3.3. Benefit/Risk Assessment

CCI

No clinically significant safety or tolerability concerns have been identified in female participants in Study CVAA up to the highest single dose administered (300 mg).

This study is being conducted prior to non-clinical evaluations assessing the risk of developmental and reproductive toxicity by LY3526318 and its active metabolite, M6. Women of child-bearing potential (WOCBP) could become pregnant during the study, and thus expose themselves and their conceptus to LY3526318 and its metabolite M6 at levels where effects are unknown. However, these risks are mitigated by non-clinical evaluations and clinical study design. Studies in two animal species that each were 28-day repeat dose designs achieving higher concentrations than planned for this clinical study, identified no adverse effects on female organs. The risk of harm to a conceptus is minimized during the early stages of pregnancy based on *in vitro* tests for genotoxicity and mutagenicity that showed no effects by LY3526318 and M6. Clinically, WOCBP must adhere to highly effective contraception and will be monitored to exclude pregnancy including documentation of the participants last menstrual period and a negative pregnancy test as per Schedule of Activities (Section 2).

More information about the known and expected benefits, risks, serious adverse events (SAEs) and reasonably anticipated AEs of LY3526318, along with safety data from CVAA study, is provided in the Investigator's Brochure ([Lilly 2019](#)).

Additional information on scientific rationale for the study design and justification for planned LY3526318 doses are provided in Sections [5.4](#) and [5.5](#), respectively.

4. Objectives and Endpoints

Table 4-1 shows the objectives and endpoints of the study.

Table 4-1 Objectives and Endpoints

Objectives	Endpoints
Primary	
To assess target engagement of TRPA1 after a single dose of LY3526318	Decrease in CA-induced dermal blood flow (DBF) relative to placebo measured by laser Doppler imaging (LDI) at 3 hours post-dose
Secondary	
To evaluate the safety and tolerability in healthy females following a single oral dose of LY3526318	
 • Treatment-emergent adverse event • Serious adverse event
To assess target engagement of TRPA1 after a single dose of LY3526318 using an alternate method	Decrease in CA-induced DBF relative to placebo measured by laser speckle contrast imaging (LSCI) at 3 hours post-dose
To assess the pharmacokinetics of LY3526318 following single oral doses of LY3526318	Summary of LY3526318 plasma concentrations by dose and time points
Exploratory	
To assess target engagement of TRPA1 after a single dose of LY3526318	
 • Decrease in CA-induced DBF relative to placebo measured by LDI at 24 hours post-dose • Decrease in CA-induced DBF relative to placebo measured by LSCI at 24 hours post-dose
To explore the relationship between LY3526318 plasma concentration and DBF in healthy females following a single oral LY3526318 dose	
 • LY3526318 plasma concentrations • DBF

5. Study Design

5.1. Overall Design

This is a Phase 1 randomized, double-blind, placebo-controlled, 4-way crossover study of LY3526318 in healthy female participants.

All participants will have 2 screening visits with the first to evaluate the health of the participant and the second visit to undergo a laser Doppler imaging (LDI) assessment to ensure a response of at least 100% increase in DBF between pre- and post-CA challenge. Following a screening period of up to 28 days, eligible participants will be confined to the clinical research unit (CRU) from Day 1 until all assessments are completed on Day 2 of each dosing period.

As summarized in [Table 5-1](#), each participant will be randomly assigned to 1 of 4 treatment sequences, with a ratio of 3 LY3526318: 1 placebo. Each participant will receive 3 doses of LY3526318 and 1 dose of placebo in a crossover manner, with at least 6 days of washout between doses. The planned dose levels of LY3526318 are anticipated not to exceed the maximum administered dose in the SAD portion of Study CVAA.

Table 5-1 **Treatment Sequence**

Sequence	Period 1	Period 2	Period 3	Period 4
P132 (n=4)	P	D1	D3	D2
12P3 (n=4)	D1	D2	P	D3
231P (n=4)	D2	D3	D1	P
3P21 (n=4)	D3	P	D2	D1

Abbreviations: D= LY3526318 dose; n = number of participants; P = placebo.

The LDI and laser speckle contrast imaging (LSCI) assessments will be performed at timepoints provided in Schedule of Activities ([Section 2](#)). The change in DBF before and after CA application will be compared between LY3526318 and placebo (refer to [Section 9.6.1](#) for further details on DBF assessment).

All assessments will be performed as defined in Schedule of Activities ([Section 2](#)).

All participants will attend a safety follow-up visit about 7 days following the last dose of study drug.

Study governance considerations are described in detail in [Appendix 3](#).

5.2. Number of Participants

Sufficient number of participants will be screened to achieve 16 randomized participants.

For purposes of this study, a participant completes the study when all scheduled procedures shown in the Schedule of Activities ([Section 2](#)) have been finished.

5.3. End of Study Definition

End of the study is the date of the last visit or last scheduled procedure shown in the Schedule of Activities ([Section 2](#)) for the last participant.

5.4. Scientific Rationale for Study Design

LY3526318 is a small molecule TRPA1 inhibitor. TRPA1 mediates neurogenic vasodilation and both TRPA1 channels and neurogenic vasodilation are activated by topical CA application. This study will assess the pharmacodynamic effects of LY3526318 following administration of single LY3526318 doses. In response to TRPA1 inhibition by LY3526318, the DBF increase induced by topical application of CA and measured by LDI and LSCI is anticipated to be reduced. Non-clinical pharmacology studies have demonstrated target engagement of other TRPA1 antagonists through changes in DBF for TRPA1 activation and antagonism ([Aubdool et al. 2016](#)). The use of two methods to measure reactive blood flow in the skin provides complementary information ([Millet et al. 2011](#)) improving the ability to translate preclinical LDI and pain reduction data to clinical data.

No SAEs are expected because doses of LY3526318 in this study were previously shown to be safe and tolerable in Study CVAA. In addition, topical application of CA has been shown to be safe and well tolerated in prior clinical studies ([Buntinx et al. 2017](#)).

5.5. Justification for Dose

The doses administered in this study will not exceed the maximum dose administered in the SAD portion of Study CVAA; which was found to be safe and well tolerated in healthy participants.

The proposed doses for this study are anticipated to be in the target engagement dose range, while providing the maximum achievable safe LY3526318 exposure, to address the study objectives.

6. Study Population

Eligibility of participants for the study will be based on the results of screening medical history, physical examination, vital signs, clinical laboratory tests, and ECG.

The nature of any conditions present at the time of the physical examination and any preexisting conditions will be documented.

Screening may occur up to 28 days prior to enrollment. If the time of screening and randomization is prolonged to greater than 28 days, the extent of rescreening will be discussed between the investigator and sponsor.

Prospective approval of protocol deviations to recruitment and enrollment criteria, also known as protocol waivers or exemptions, are not permitted.

6.1. Inclusion Criteria

Participants are eligible for inclusion in the study only if they meet all of the following criteria at screening. The timeframes included in the following criteria are relative to screening unless otherwise noted.

1. Healthy female participants as determined by medical history and physical examination.
 - a. Female participants must be nonpregnant and not lactating, or of nonchildbearing potential (either surgically sterilized [e.g. tubal occlusion, hysterectomy, bilateral salpingectomy] or physiologically incapable of becoming pregnant, or postmenopausal with amenorrhea for at least 12 consecutive months)
 - b. Nonpregnancy will be confirmed for all female participants through a serum pregnancy test at screening, at (each) admission to the CRU and, at other time points specified in the Schedule of Activities (Section 2). Follicle-stimulating hormone will be tested at screening for all female participants.
 - c. Healthy female participants of child-bearing potential who have a fertile male sexual partner must be willing and able to practice effective contraception from screening visit \leq 28 days to 30 days after the final visit.
 - d. Sexually active participants must use a combination of 2 of the following methods of contraception, including so called 'barrier' methods:
 - i. Hormonal contraceptive associated with inhibition of ovulation (oral, transdermal patches, vaginal or injectable)
 - ii. Intrauterine device with or without hormones
 - iii. Condom, diaphragm or cervical cap ('barrier' methods)

Contraceptive requirements do not apply for participants who are sexually abstinent or exclusively in same-sex relationships.

2. Have given written informed consent, approved by the sponsor and the Institutional Review Board (IRB) governing the site, prior to any study-specific procedures
3. Aged 18 to 45 years, inclusive.
4. Have a body-mass index of 18 to 30 kg/m², inclusive.
5. Are reliable and willing to make themselves available for the duration of the study.
6. Are willing to follow CRU specific study procedures including,
 - a. no drugs (except study drug, hormonal contraceptives) 7 days prior to each DBF assessment and until discharge from CRU;
 - b. no chocolate, alcohol, or caffeine containing products 24 hours prior to initiation of each DBF assessment and until discharge from CRU;
 - c. a complete 4 hour fast (water is allowed) prior to initiation of each DBF assessment.
7. Have suitable skin characteristics for the dermal CA challenge (as determined by CRU-staff judgment) and have demonstrated at least a 100% increase in dermal flow following CA challenge as part of the screening procedures and measured through LDI.
8. Have clinical laboratory test results within normal reference range for the population or CRU, or results with acceptable deviations that are judged not clinically significant by the investigator.

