6.2. Exclusion Criteria

Participants will be excluded from study enrollment if they meet any of the following criteria at screening:

1. Are male.
2. Are currently enrolled in or discontinued within the last 30 days or 5 half-lives of the study drug (whichever is longer), from a clinical study involving an investigational product or any other type of medical research judged not to be scientifically or medically compatible with this study.
3. Have received treatment with biological agents (such as monoclonal antibodies, including marketed drugs) within 3 months or 5 half-lives (whichever is longer) prior to dosing.
4. Have previously completed or withdrawn from this study or any other study investigating this study drug.
5. Have a history or presence of medical illness including, but not limited to, any cardiovascular, hepatic, respiratory, hematological, endocrine, psychiatric or neurological disease, convulsions, or any clinically significant laboratory abnormality that, in the judgment of the investigator, indicate a medical problem that would preclude study participation.
6. Have an abnormality in the 12-lead ECG that, in the opinion of the investigator, increases the risks associated with participating in the study. In addition, participants with the following findings will be excluded:

- a. confirmed Frederica's corrected QT interval >470 msec One repeat ECG may be performed if required.
7. Have a history of clinically significant multiple or severe drug allergies or severe post-treatment hypersensitivity reactions, which in the opinion of the investigator may hamper participation in the study.
8. Are investigator or CRU personnel directly affiliated with this study or are immediate family members of investigator or CRU personnel. Immediate family is defined as a spouse, parent, child or sibling, whether biological or legally adopted.
9. Are Eli Lilly and Company (Lilly) employees or contractors or an immediate family member of employees or contractors.
10. Show evidence of human immunodeficiency virus (HIV) and/or positive human HIV antibodies, hepatitis C and/or positive hepatitis C antibody, or hepatitis B and/or positive hepatitis B surface antigen.
11. Have donated blood of more than 500 mL within the previous month.
12. Have an abnormal blood pressure (supine) defined as a diastolic blood pressure >90 or <50 mmHg and/or a systolic blood pressure >140 or <90 mmHg.

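### As worded, inclusion 1a makes nonchildbearing potential an alternative to the lactation restriction, so no explicit criterion bars a nonpregnant, breastfeeding woman who is surgically sterile.

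*Protocol*

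**What the plan says.** Section 6.1 opens with the rule that "Participants are eligible for inclusion in the study only if they meet all of the following criteria at screening". Criterion 1a then states: "Female participants must be nonpregnant and not lactating, or of nonchildbearing potential (either surgically sterilized [e.g. tubal occlusion", and goes on to name hysterectomy and bilateral salpingectomy as further examples of sterilization, and physiological incapacity and postmenopausal status as further forms of nonchildbearing potential. Criterion 1b deals with pregnancy separately and for everyone: "Nonpregnancy will be confirmed for all female participants through a serum pregnancy test at screening", with further tests at each admission and at other scheduled times. Criterion 3 sets the age range: "Aged 18 to 45 years, inclusive".

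Section 6.2 says that "Participants will be excluded from study enrollment if they meet any of the following criteria at screening" and lists 18 criteria. None mentions lactation or breastfeeding. The nearest is criterion 5, which concerns illness or a clinically significant laboratory abnormality that, in the investigator's judgment, would "indicate a medical problem that would preclude study participation".

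Section 3.3 records the state of the reproductive evidence: "This study is being conducted prior to non-clinical evaluations assessing the risk of developmental and reproductive toxicity by LY3526318 and its active metabolite, M6". The readable text there goes on to discuss pregnancy in women of childbearing potential and exposure of a conceptus.

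**The concern.** A restriction on lactation is normally a condition on every participant. Here it sits in one arm of an either/or, and the other arm is met by sterilization alone. Tubal occlusion and bilateral salpingectomy, both named in 1a, do not stop a woman breastfeeding, and the age range includes women who may be doing so.

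At stake is exposure of a nursing infant, a third party who is neither consented nor monitored, to a compound and an active metabolite whose developmental and reproductive toxicity had not been evaluated when the protocol was written. Participants are discharged on Day 2 of each period, and the readable protocol gives no instruction about breastfeeding after that.

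**Working it through.** No figure is involved, so the check is a reading of the criterion's logic followed by a search for any other text that would close the gap.

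**Step 1. Logic of 1a.** Let N = nonpregnant, L = not lactating, S = of nonchildbearing potential. The sentence can be grouped in two ways:

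- Grouping A: (N and L) or S
- Grouping B: N and (L or S)

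| Participant | N | L | S | A | B |
|---|---|---|---|---|---|
| Breastfeeding, tubal occlusion | true | false | true | met | met |
| Breastfeeding, of childbearing potential | true | false | false | not met | not met |
| Not breastfeeding, tubal occlusion | true | true | true | met | met |

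For the first row, A gives (true and false) or true = true, and B gives true and (false or true) = true. The result does not depend on the grouping. The second row shows that the restriction works for women of childbearing potential; the gap is confined to those of nonchildbearing potential.

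**Step 2. Pregnancy and lactation side by side.** Under grouping A the same or would also release a sterile woman from the nonpregnancy condition. Other text closes that half and leaves the lactation half open:

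| Where | Pregnancy | Lactation |
|---|---|---|
| 6.1, criterion 1b | serum test for all participants | not mentioned |
| 6.2, 18 exclusions | not listed (1b covers it) | not mentioned |
| Section 8, discontinuation | a positive test in a participant of childbearing potential during a unit stay leads to discontinuation | not mentioned |
| Schedule of Activities | repeated tests | no item |

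The only other appearance of lactation is in Appendix 6, where 1a is reprinted with the same wording. The amendment described there changed 1.d.i and did not touch 1a. The SAP does not mention lactation.

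**Step 3. Number of active doses.** Every sequence in Table 5-1 contains P, D1, D2 and D3 once each. That is 4 periods − 1 placebo = 3 active doses per participant.

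**Step 4. Effect of the change.** If 1a becomes N and L for everyone, the first row gives true and false = false, and she is not eligible. The third row gives true and true = true, so sterile women who are not breastfeeding are still admitted.

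**The case against.** The strongest answer is that nobody meant this. Criterion 1b treats nonpregnancy as universal, which suggests that its partner in 1a was meant to be universal too. That stands. A reader might infer from 1a that the sponsor chose to admit breastfeeding women, and the documents do not support that.

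A second answer is that meeting the criteria is necessary for entry, not sufficient. Participants must also be judged healthy from history and examination, and an investigator may decline to enrol someone. This stands as well. A reader might infer from the ban on waivers in Section 6 that the wording alone decides eligibility, but that ban stops sites enrolling people who fail a criterion and does not oblige them to enrol everyone who passes. What remains is that no explicit criterion bars her. Lactation is not an illness or a laboratory abnormality, so exclusion 5 does not clearly reach it.

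A third answer is that Section 3.3 says nothing about a nursing infant. It speaks of women who become pregnant and of a conceptus, and it cites 28-day studies in two species with no adverse effect on female organs and *in vitro* tests showing no genotoxicity or mutagenicity. That is correct. Section 3.3 shows that the reproductive evidence was incomplete; it does not show a risk through milk. Part of that section is redacted, and the consent form and Investigator's Brochure are not available here, so they may address lactation. The eligibility lists themselves show no redaction.

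**Conclusion.** The point holds as one of wording. Read either way, 1a admits a nonpregnant, breastfeeding woman who is surgically sterile, and nothing else in the readable protocol explicitly excludes her. The likely intent was the opposite.

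The size is small. Such a woman would also have to meet every other criterion, including the cinnamaldehyde response at screening, in a trial of 16 randomized participants. The documents give no basis for a count. She would receive three active doses and one placebo; a reader might infer four drug exposures from the four dosing periods, but Table 5-1 rules that out. How much drug or M6 would reach an infant is unknown from these documents, so possible infant exposure is an assumption, not a finding.

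There is no effect on the endpoint, alpha, power or analysis. It is a minor safety-wording correction.

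**What to change.** Reword 1a so that being nonpregnant and not lactating is required of every participant, whatever her childbearing potential. Alternatively, leave 1a as it stands and add lactation as an exclusion in 6.2. Either closes the gap. If the sponsor did intend an exception for women of nonchildbearing potential, the protocol should say so and Section 3.3 should give the reason.

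Leave 1c and 1d unchanged. It is tempting to let childbearing potential govern contraception as part of the same edit, but 1d applies to sexually active participants without limiting it to those of childbearing potential. Tying it to childbearing potential would change who must use contraception, which is a separate decision.

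The cost is one line in a protocol amendment, with a likely negligible effect on recruiting 16 women and no change to the SAP.
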